7.3.3 D1 Week 3 (Optional Visit)

Note: This is an optional visit that will occur if the condition of the subject is such that follow up on D1/week 3 is considered medically necessary by the investigator. Clinical labs may be performed as needed but are not required.

Clinical evaluation: History, physical examination

Laboratory studies:

- CBC with differential and platelets (performed as needed)
- CMP: BUN, creatinine, Na, K, Cl, CO2, glucose, calcium, albumin, total protein, total bilirubin, ALT, AST, alkaline phosphatase (performed as needed)
- Blood Sample for Correlative Studies (see section 7.5)
 - Function and persistence studies: optional
 - Quantitative PCR: optional
 - Genetic analysis (optional at this time point see Section 7.5.5)

Toxicity: Toxicity will be assessed according to the NCI CTCAE v. 4.0, CRS Toxicity Grading Scale (See APPENDIX VIII- CRS Toxicity Grading Scale and Management Guidelines).

Patient reported outcome questionnaires for adult subjects (optional): PROMIS Global Health Scale, PROMIS Physical Function, and selected questions from NCI PRO-CTCAE

7.3.4 D1 Week 4

Clinical evaluation: History, physical examination

Laboratory studies:

- CBC with differential and platelets
- CMP: BUN, creatinine, Na, K, Cl, CO2, glucose, calcium, albumin, total protein, total bilirubin, ALT, AST, alkaline phosphatase
- Blood Sample for Correlative Studies (see section 7.5)
 - Function and persistence studies
 - Quantitative PCR
 - Genetic analysis (see Section 7.5.5)

Toxicity: Toxicity will be assessed according to the NCI CTCAE v. 4.0, CRS Toxicity Grading Scale (See APPENDIX VIII- CRS Toxicity Grading Scale and Management Guidelines).

Patient reported outcome questionnaires for adult subjects (optional): PROMIS Global Health Scale, PROMIS Physical Function, and selected questions from NCI PRO-CTCAE

7.3.5 D1 Week 6

Clinical evaluation: History, physical examination

Laboratory studies:

- CBC with differential and platelets
- Dermatology consult needed for cutaneous lymphomas only
- Blood taken for leukemia profile and flow cytometry (mycosis fungiodes and Sezary syndrome patients only).
- CMP: BUN, creatinine, Na, K, Cl, CO2, glucose, calcium, albumin, total protein, total bilirubin, ALT, AST, alkaline phosphatase
- Blood Sample for Correlative Studies (see section 7.5)
 - Function and persistence studies
 - Quantitative PCR
 - HAMA testing
 - Genetic analysis (see Section 7.5.5)

Imaging: Imaging to assess disease status (PET, CT scans, MRI, nuclear imaging) 6-8 weeks following the infusion. The choice of imaging will depend on what studies have been most informative in following the subject's disease. If subject has cutaneous lymphoma see section 7.1.1 for details.

Toxicity: Toxicity will be assessed according to the NCI CTCAE v. 4.0, CRS Toxicity Grading Scale (See APPENDIX VIII- CRS Toxicity Grading Scale and Management Guidelines).

Patient reported outcome questionnaires for adult subjects (optional): PROMIS Global Health Scale, PROMIS Physical Function, and selected questions from NCI PRO-CTCAE

7.3.6 D1 Month 3

Clinical evaluation: history, physical examination, Karnofsky or Lansky performance status.

Laboratory studies:

- CBC with differential and platelets
- CMP: BUN, creatinine, Na, K, Cl, CO2, glucose, calcium, albumin, total protein, total bilirubin, ALT, AST, alkaline phosphatase
- Blood taken for leukemia profile and flow cytometry (mycosis fundgiodes and Sezary syndrome patients only)
- Thyroid function
- Blood Sample for Correlative Studies (see section 7.5)
 - Function and persistence studies
 - Quantitative PCR
 - Genetic analysis (see Section 7.5.5)

Patient reported outcome questionnaires for adult subjects (optional): PROMIS Global Health Scale, PROMIS Physical Function, and selected questions from NCI PRO-CTCAE

7.3.7 D1 Month 6

Clinical evaluation: history, physical examination, Karnofsky or Lansky performance status.

Laboratory studies:

- CBC with differential and platelets
- CMP: BUN, creatinine, Na, K, Cl, CO2, glucose, calcium, albumin, total protein, total bilirubin, ALT, AST, alkaline phosphatase

- Blood Sample for Correlative Studies (see section 7.5)
 - Function and persistence studies
 - Quantitative PCR
 - Genetic analysis (see Section 7.5.5)

Patient reported outcome questionnaires for adult subjects (optional): PROMIS Global Health Scale, PROMIS Physical Function, and selected questions from NCI PRO-CTCAE

Imaging: Imaging to assess progression (PET, CT scans, MRI, nuclear imaging) at 6 months \pm 1 month following the infusion. The choice of imaging will depend on what studies have been most informative in following the subject's disease.

7.3.8 D1 Month 9

Clinical evaluation: history, physical examination, Karnofsky or Lansky performance status.

Laboratory studies:

- CBC with differential and platelets
- CMP: BUN, creatinine, Na, K, Cl, CO2, glucose, calcium, albumin, total protein, total bilirubin, ALT, AST, alkaline phosphatase
- Blood Sample for Correlative Studies (see section 7.5)
 - Function and persistence studies
 - Quantitative PCR
 - Genetic analysis (see Section 7.5.5)

Patient reported outcome questionnaires for adult subjects (optional): PROMIS Global Health Scale, PROMIS Physical Function, and selected questions from NCI PRO-CTCAE

7.3.9 D1 Month 12

Clinical evaluation: history, physical examination, Karnofsky or Lansky performance status.

Laboratory studies:

- CBC with differential and platelets
- CMP: BUN, creatinine, Na, K, Cl, CO2, glucose, calcium, albumin, total protein, total bilirubin, ALT, AST, alkaline phosphatase
- Thyroid function
- Blood Sample for Correlative Studies (see section 7.5)
 - Function and persistence studies
 - o Quantitative PCR
 - Genetic analysis (see Section 7.5.5)

Patient reported outcome questionnaires for adult subjects (optional): PROMIS Global Health Scale, PROMIS Physical Function, and selected questions from NCI PRO-CTCAE

Imaging: Imaging to assess progression (PET, CT scans, MRI, nuclear imaging) at 6 months +/- 1 month following the infusion. The choice of imaging will depend on what studies have been most informative in following the patient's disease.

7.4 Long Term Follow-Up

Quantitative real-time PCR to detect transgene copy numbers will be collected preinfusion, 3-4 hours post infusion, 1, 2, 3, 4 and 6 weeks post- T cell infusion, 3, 6, 9, and 12 months post- T cell infusion and then yearly for a total of 15 years. If transgene copy number is >1000 copies/1µg DNA, then samples to determine transgene copy numbers will be collected every 6 months after the first year until transgene copy number is <1000 copies/1µg DNA at which time samples will then be collected yearly for a total of 15 years.

If at 6 months post- T cell infusion, transgene is detected at >0.5% by flow cytometry then PCR to detect retroviral integrant clonality and integrant locus will be performed and will continue every 6 months until detection is <0.5%. Samples will then be collected annually and may be archived for a total of 15 years. If the level of detection is less than 0.5%, samples will be collected annually and may be archived. Follow up will continue for 15 years.

If a subject develops a delayed adverse event that is related to the trial drug, then more frequent (2-4 times per year) clinical observation may be indicated. Appropriate follow up will be conducted based on a particular subject's prior test results. The investigator will determine the additional testing and sample collection that is needed. New malignancies and delayed adverse events will be recorded during long term follow-up.

Regarding annual genetic analysis through year 15, see Section 7.5.5.

7.5 Correlative Studies: Tests of Function, Persistence and Safety

The following investigations will be used to monitor function and persistence in peripheral blood and safety of transduced T-cells at time-points indicated in the Time and Events Table. A maximum of the lesser of 50 mL or 2 mL/kg of body weight of blood will be drawn on any one day for these assays. If a subject's hemoglobin is less than 8.0 g/dL at any of the evaluation times, the amount of blood drawn for the evaluation will be reduced and may be obtained over more than one venipuncture, if necessary. If there is insufficient blood, samples archived for RCR testing if needed, and Quantitative real-time PCR, will be the first priorities. Note: the studies are not necessarily performed at the time of blood collection. Correlative blood sample collection will cease if the samples are no longer required for persistence and function or clonality analysis.

7.5.1 Function and Persistence Studies

These will include immunophenotyping (when possible) as well as quantitative polymerase chain reaction (qPCR) to detect transgene persistence. When applicable, functional assays will be performed, such as in vitro reactivation of PBMCs in subjects for whom the appropriate reagents are available.

7.5.2 RCR Testing by PCR

Subject blood samples will be collected pre-infusion and stored. Samples will also be collected and both samples analyzed if the subject develops any of the following long-term gene therapy side effects:

- New malignancy(ies)
- Exacerbation of a pre-existing or new incidence of a neurologic disorder
- Exacerbation of a prior or new incidence of a rheumatologic or other autoimmune disorder
- New incidence of a hematologic disorder
- New incidence of infection (potentially product-related).

7.5.3 Clonality

If the transgene is detected at > 0.5% by either flow cytometry (if feasible) or by qPCR at the 6-month sample collection timepoint, then PCR to detect retroviral integrant clonality and integrant locus will be performed. This analysis will continue every 6 months until detection is < 0.5% for up to 5 years. After this time, it will be collected

annually. If the level of detection is < 0.5% at 6-months, samples will be collected annually and may be archived. Samples will no longer be collected if detection is < 0.5% for more than 1 consecutive testing period.

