1.6 Study Design and Rationale

ASCT may be the only curative option for subjects with refractory/relapsed hematological malignancies. Despite ASCT, disease recurrence remains the major cause of treatment failure. Hence development of non-toxic consolidation treatments after transplant remains a highly desirable objective, and the adoptive transfer of CTLs is one promising approach [64-67].

In this Phase I multicenter study, peripheral blood will be collected for production of ATLCAR.CD30 cells in subjects with CD30⁺ lymphoma at high risk of relapse post-transplant, and scheduled to undergo ASCT. Three dose levels will be evaluated to identify the MTD in this population: Level $1 = 2 \times 10^7 \text{ CAR}^+ \text{ T cells/m}^2$; Level $2 = 1 \times 10^8/\text{m}^2$; Level $3 = 2 \times 10^8/\text{m}^2$. The total number of cells infused will be calculated on the number of CAR-T cells as requested by the FDA. Similar to the prior phase I

LCCC1524-ATL
Administration of T lymphocytes Expressing the CD30 Chimeric Antigen Receptor (CAR)
for Prevention of Relapse of CD30+ Lymphomas after High Dose Therapy and Autologous
Stem Transplantation (ATLAS)
ATLCAR.CD30

summarized in section 1.5.5, we will monitor the persistence of these infused cells in the peripheral blood of the subjects and whenever lymph nodes are biopsied as per routine clinical care during the first year after treatment at the tumor site by measuring the level of the transgene by both phenotypic and molecular analyses. Currently, we can regularly detect a single transduced cell in 50,000 peripheral blood mononuclear cells by real-time PCR amplification. Moreover, because gene persistence and expression may not correlate with antitumor effector function, we will also determine the functionality of the peripheral blood T cells *ex vivo*.

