 - 11. Correlative analysis will include the following. Correlative blood sample collection will cease if the samples are no longer required for persistence and function or clonality analysis.
- a. **Persistence and Function:** The analyses will be used to monitor persistence and function (if applicable) in peripheral blood and will include immunophenotyping as well as quantitative polymerase chain reaction (qPCR) to detect transgene persistence and

functional assays such as in vitro reactivation of PBMCs in subjects for whom the appropriate reagents are available. Quantitative real-time PCR to detect the transgenes will be collected pre-lymphodepletion, pre-dosing (approximately 19 mL of blood), at 3 - 4 hours post infusion (approximately 16 mL of blood), 1, 2-, 3-, 4- and 6-weeks visits post each T-cell infusion and then at the 3-, 6-, 9-, and 12-months visits. Persistence and function will be continued for up to one-year post-CAR T cell infusion. If a transgene copy number is > 500 copies/µg DNA, then samples to determine transgene copy number is < 500 copies/µg DNA at which time samples will then be collected yearly for up to a total of 15 years. If transgene is no longer detectable by PCR after 1-year post-final CAR T infusion, then collection for function and persistence will discontinue. See Section 7.5.1 and the Laboratory Manual for the amount of blood collected/type of tube used for all of the correlative studies.

- b. **Clonality:** If the transgene is detected at > 0.5% either flow cytometry (if feasible) or by qPCR at the 6-month sample collection timepoint, then PCR to detect retroviral integrant clonality and integrant locus will be performed. This analysis will continue every 6 months until detection is < 0.5% for up to 5 years. After this time, it will be collected annually. If the level of detection is < 0.5% at 6-months, samples will be collected annually and may be archived. Samples will no longer be collected if detection is < 0.5% for more than 1 consecutive testing period. See Section 7.5.3.

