Our proposal should have a very different risk profile than that reported by Morgan and colleagues and summarized in Section 1.5.2 [45]. Large doses of transduced T-cells (in the order of 10^{10} cells) were administered to patients that received prior lymphodepletion and no leukemogenesis occurred. Although the inclusion of the CD28 endodomain in the CAR may enhance proliferation of transgenic T-cells in response to the CD30 antigen, there is no reason to believe this effect will lead to uncontrolled Tcell expansion. Ex vivo and published in vivo data using several artificial T-cell receptors shows that CD28 sustains limited and temporary expansion over approximately 3 weeks[82]. Our recent clinical trial using CD19-CAR-specific T-cells including the CD28 endodomain also indicates that these T-cells expand significantly for only 2-3 weeks and then they decline without evidence of further expansion [26]. Thereafter, the cells maintain the expression of the transgene, but proliferate further only in the presence of both antigen and exogenous cytokines.

To date, more than 200 patients have received genetically modified cells in clinical trials including patients we have treated on our protocols using retrovirally marked autologous marrow[83] or retrovirally marked EBV-CTLs[64, 84, 85]. In none of these has malignancy caused by retroviral transduction been reported. However, there is a

possibility that the vector could randomly integrate into a site that could lead to leukemogenesis.

Current intensive regimens to treat relapsed lymphoma describe subsequent secondary malignancy rates in excess of 10%[86]. In light of this, the natural history and poor prognosis of advanced lymphoma, and given the entire previous experience with retroviral gene therapy, we feel that the risks of retroviral induced leukemogenesis are small and are justified in this patient group.

Cross-reactivity

CD30 can be expressed by activated T-cells and NK cells. Direct toxicity to these cells due to targeting of their CD30 molecules by transduced cells is possible. In case of this eventuality, a number of therapeutic maneuvers are available. Corticosteroids in doses used to treat graft-versus host-disease (GvHD) will deplete the majority of circulating transduced cells.

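### Clonality testing can be triggered only by the month-6 transgene level: no later rise starts or restarts it, so a subject below 0.5% at month 6 has no level-based trigger for the remaining 14.5 of 15 years

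*Combined protocol and SAP*

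**What the plan says.** **Trigger.** Section 7.5.3 requires clonality and integrant-locus PCR if the transgene is above 0.5%, measured by flow cytometry where that can be done, or else "by qPCR at the 6-month sample collection timepoint, then PCR to detect retroviral integrant clonality and integrant locus will be performed". Footnote 11b to the Time and Events Table (section 4.2) says the same. Section 7.4 and Appendix IV footnote 3b also use month 6 and 0.5%, but by flow cytometry only.

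**Above 0.5% at month 6.** "This analysis will continue every 6 months until detection is < 0.5% for up to 5 years"; collection is then annual.

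**Below 0.5% at month 6.** "If the level of detection is < 0.5% at 6-months, samples will be collected annually and may be archived". No analysis is required.

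**End of sampling.** Section 7.5.3, footnote 11b and Appendix IV 3b add: "Samples will no longer be collected if detection is < 0.5% for more than 1 consecutive testing period". Section 7.4 has no such rule and keeps annual, archivable samples for 15 years.

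**Persistence qPCR.** Footnote 11a and Appendix IV 3a follow subjects above 500 copies/µg DNA every 6 months after year 1 until they fall below that level, "at which time samples will then be collected yearly for up to a total of 15 years". Collection for persistence ends if the transgene is undetectable after year 1. Section 7.4 instead schedules yearly qPCR for all subjects to year 15, with a threshold of 1000 copies/µg.

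**The risk.** Section 8.3 leaves open a "possibility that the vector could randomly integrate into a site that could lead to leukemogenesis".

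**The concern.** The rule uses later transgene levels to stop sampling but never to start testing. Footnote 11a or section 7.4 may record a rise at year 3 or year 8, yet nothing tells the laboratory or the investigator to ask whether the expanding population is clonal.

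The protocol's own reasoning makes this relevant. Section 1.5.2 says that retroviral integration can, rarely, cause uncontrolled proliferation. Section 8.3 describes leukemia associated with a single integrant in 4 of 11 patients in an earlier gene therapy trial, while arguing that this trial's risk is much lower. It also reports that comparable CAR-T cells with the CD28 endodomain expand for 2–3 weeks and then decline without expanding further. A rise after month 6 would depart from that pattern. At stake is long-term safety surveillance; dose finding, sample size and the primary endpoint are not affected.

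**Working it through.** The documents state no operating figure for clonality monitoring, so there is none to reproduce. The check lays each branch of the rule on the 15-year follow-up of section 6.2.

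**1. Below 0.5% at month 6: time without a trigger.** Follow-up minus trigger time = 15 − 0.5 = 14.5 years (14.5/15 = 96.7%). This is time without a level-based trigger, not time without samples.

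**2. Same subject: time without clonality samples.** The stop rule in section 7.5.3 can mean two or three successive low results, and the annual draw can be counted from infusion or from month 6.

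| Reading of the rule | Low results at month | Sampling ends (year) | Years unsampled |
|---|---|---|---|
| Two low results, from infusion | 6, 12 | 1.0 | 15 − 1.0 = 14.0 |
| Two low results, from month 6 | 6, 18 | 1.5 | 15 − 1.5 = 13.5 |
| Three low results, from infusion | 6, 12, 24 | 2.0 | 15 − 2.0 = 13.0 |
| Three low results, from month 6 | 6, 18, 30 | 2.5 | 15 − 2.5 = 12.5 |
| Section 7.4 | no stop rule | 15 | 0 |

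**3. Above 0.5% at month 6, later below.** With tests every 6 months from month 6 up to and including the first low result at month m, the number of tests is m/6 and the time left without a re-trigger is 15 − m/12 years.

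| First below 0.5% (month) | Tests | Years without a re-trigger |
|---|---|---|
| 12 | 2 | 14 |
| 24 | 4 | 13 |
| 36 | 6 | 12 |
| 60 | 10 | 10 |

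**4. Always above 0.5%.** Ten six-monthly tests to year 5 (60/6), then ten annual collections to year 15. The 14.5-year gap does not apply.

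**5. Other routes to a clonality answer.**
- Section 7.5.5 permits yearly integration-site analysis to year 15, but it is optional, relates integration site to cell behavior, and is not tied to a transgene level.
- Section 7.5.2 responds to a new malignancy and other listed events, but with testing for replication-competent retrovirus, which is a different question.
- Section 7.4 and footnote 17 leave additional testing to the investigator when a related delayed adverse event occurs.

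None of these requires a clonality test because the transgene has risen.

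**The case against.** The strongest reply is that the month-6 rule appears in four places and looks deliberate. Section 8.3 reports more than 200 recipients of genetically modified cells with no malignancy caused by retroviral transduction, and judges the risk small. The investigator is not powerless: section 7.4 ties follow-up to a subject's prior test results, and section 9.1.1 counts an abnormal laboratory finding as an adverse event, so a rising transgene could prompt extra work. Integration analysis is also available each year.

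These points lower the priority but leave the gap open. A small risk is still the one this assay addresses, and discretion and optional research analyses do not amount to a written trigger.

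The reply does defeat several stronger readings that a reader might infer:

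- That clonality surveillance ends at month 6. Section 7.5.3 needs more than one low period before sampling ends, and section 7.4 never ends it.
- That 14.5 years applies to everyone. Subjects above 0.5% at month 6 continue to be tested while they remain above it, up to year 5.
- That nothing could be done before a malignancy is diagnosed. Any related delayed adverse event opens investigator-directed testing.
- That a rising transgene is known to be the first sign of outgrowth, or that leukemogenesis is the stated reason for 15 years of follow-up. The documents say neither.
- That the distance between 0.5% and the sensitivity in section 1.6 ("we can regularly detect a single transduced cell in 50,000 peripheral blood mononuclear cells by real-time PCR amplification") measures how far a level could climb unseen. Section 7.5.3 gives no denominator for its percentage, so the two figures cannot safely be compared.

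**Conclusion.** The concern holds in a limited form. In all four passages the clonality test depends on the month-6 level alone, and no later rise starts or restarts it. The gap is 14.5 of 15 years for subjects below 0.5% at month 6, and 10 to 14 years in the worked examples for subjects who start above 0.5% and then fall below. These figures assume full 15-year follow-up and six-monthly intervals counted from infusion.

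There is also a conflict in the text. Section 7.4 differs from section 7.5.3, footnote 11b and Appendix IV 3b on whether sampling ends. Section 7.4 and Appendix IV 3b allow flow cytometry only, whereas section 7.5.3 and footnote 11b allow flow or qPCR. The same subject could have between 0 and 14.0 years without clonality samples, depending on which passage a site follows.

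The documents do not show how many subjects would have a late rise or what risk would be missed, so no event rate is claimed. This should be corrected by amendment, as a gap in safety monitoring.

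**What to change.** Amend section 7.5.3, section 7.4, footnote 11b and Appendix IV footnote 3b together:

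1. Apply the existing threshold of more than 0.5% to every persistence result from month 6 onward.
2. State that clonality testing starts, or reopens, when a later result exceeds 0.5%, including in subjects whose routine clonality sampling has ended.
3. Use one sampling stop rule, and say whether it means two or three successive low results.
4. Use one detection method. Persistence qPCR is reported in copies/µg DNA and the trigger is a percentage, so state the conversion or refer to where the laboratory manual gives it.

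No additional fold-change criterion is needed.

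The cost is a few extra integration assays on samples already collected under the persistence schedule, with no new visits. Two limits remain. Subjects whose sampling has ended because the transgene is undetectable stay uncovered. Footnote 11a also does not say whether a subject who is detectable after year 1 but never above 500 copies/µg keeps giving yearly samples, whereas section 7.4 implies yes. The amendment should settle that, because the new trigger works only where a later result exists.
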